10.2 Data Collection

Data collection and study procedures are outlined in Table 4: Data collection and study procedure requirements at subject visits.

Table 4: Data collection and study procedure requirements at subject visits

Study Procedure	Baseline	Implant	7-Day	1-Month	2-Month	3-Month	6-Month	12-Month	24-Month	Unscheduled	System Modification ^a
Informed Consent ^b	X										
Medical History	X										
Eligibility Assessment	X										
MESA Questionnaire	X										
Pregnancy Test ^c	X										
Neurostimulator Implant		X									X ^d
Ultrasound Images ^d		X									X
Sensory/Motor Thresholds		X	X	X	X	X	X	X	X ^d	X	
Voiding Diary	X			X	X	X	X	X	X ^d	X ^d	
OAB-q/ [REDACTED]/UPS Questionnaires	X					X	X	X	X		
<hr/>											
Programming/Device Data (e.g., Session Reports, Usage Reports)		X	X	X	X	X	X	X	X	X ^d	X
Periodic Check-in Calls ^f		X	X	X	X	X	X	X	X		
Neurostimulator Explant											X ^d
OAB Medication Usage, Study Deviations, Adverse Events, and Deaths											As they occur
Device Deficiencies											As they occur

^a 7-day post-procedure visit and 1-month phone call will be completed following any system modification/explant procedures

^b Informed Consent must be completed prior to any study-related procedures including the Baseline voiding diary.

^c Females of Child-bearing potential only

^d If applicable

^f Calls are recommended approximately 1 week prior to study visits, within 48 hours after each study visit and monthly. Monthly calls are recommended following the 3-month follow-up visit.

10.3 Scheduled Follow-up Visit Windows

Should a subject miss a visit or the visit falls outside the pre-specified window, a study deviation must be reported, and the original follow-up schedule maintained for subsequent visits.

Data analyses include follow-up visits, regardless of whether the visit occurs within the window. Therefore, a late visit is preferred over a missed visit but must be accompanied with a reported study deviation. Follow-up visit windows are listed in Table 5 and are based on days post-implant.

Table 5: Study Follow-up Visit Windows

Study Follow-up Visit	Window (Calculated calendar days post-implant; implant is Day 0)		
	Window Start (days post-implant)	Target (days post-implant)	Window End (days post-implant)
7-Day Post-Procedure Follow-up Visit	4 days	7 days	10 days
1-Month Follow-up Visit	20 days	30 days	40 days
2-Month Follow-up Visit	46 days	60 days	74 days
3-Month Follow-up Visit	76 days	90 days	104 days
6-Month Follow-up Visit	150 days	180 days	210 days
12-Month Follow-up Visit	330 days	360 days	390 days
24-Month Follow-up Visit	660 days	720 days	780 days

10.4 Subject Screening

Subjects may be recruited through the investigator's practice, referring physicians, and advertisements in the public. Potential subjects may be identified through chart reviews or as new or existing patients attending clinic visits. If subjects are referred from outside the investigator's practice, sites are to ensure that appropriate release for access to the subject's records (paper and/or electronic) is obtained. Any subject recruitment materials disseminated to subjects (advertisements, handouts, posters, social media) must be approved by the IRB prior to use.

All subjects must be consented in accordance with the protocol prior to any study-specific procedures. Recruited subjects will be screened by the Principal Investigator or authorized site personnel by reviewing the study's inclusion and exclusion criteria.

A pre-screen (recruitment) log will be available to track subjects screened but not consented for the study. No subject-specific information will be collected on this log, only the date of review and the reason for the screen failure.

A screening log will be completed by the site to maintain a cumulative log of all screened subjects with reason for any screening failures.

The Investigator will maintain a listing of all subjects enrolled in the study (Subject Identification & Enrollment Log).

10.5 Prior and Concomitant Medications/Therapies

Restrictions related to use of OAB treatments prior to enrollment in the study is outlined in the study-specific exclusion criteria. Subjects will be prohibited from taking overactive bladder medications and starting any additional advanced therapies for OAB during the first 12 months of their study participation. If the subject is consented while taking overactive bladder medications, they must have a washout of 2 weeks prior to starting the baseline voiding diary and the baseline Overactive Bladder Quality of Life Questionnaire (OAB-q). Any overactive bladder medications will be captured on a study-specific medication log, and any new advanced therapies for OAB will be captured within the follow-up visit. If additional treatment is added prior to the 12-month follow-up visit, a protocol deviation is required. Throughout the study, a voiding diary is required prior to starting any OAB medication or advanced therapies to confirm the patient is a non-responder (< 50% improvement from baseline) to tibial neuromodulation therapy. If additional treatment is added without confirmation of non-response to the therapy documented on a voiding diary, a deviation is required.

10.6 Subject Consent

Informed consent is defined as a legally effective documented confirmation of a subject's voluntary agreement to participate in a particular study after information has been given and explained to the subject on all aspects of the study that are relevant to the subject's decision to participate. This process includes obtaining an IC form and an Authorization to Use and Disclose Personal Health Information/Research Authorization as required by law that has been approved by the study site's IRB and signed and dated by the subject. A subject may only consent after information has been given and explained to the subject on all aspects of the clinical investigation that are relevant to the subject's decision to participate.

Prior to enrolling subjects, the IC and the Authorization to Use and Disclose Personal Health Information/Research Authorization/other privacy language as required by law must be approved by the IRB. The document(s) must be controlled (i.e., versioned and/or dated) to ensure it is clear which version(s) were approved by the IRB.

The investigator must notify the subject of any significant new findings about the study that become available during the course of the study which are pertinent to the safety and well-being of the subject,

as this could impact a subject's willingness to participate in the study. If relevant, consent may be requested from subjects to confirm their continued participation.

Prior to initiation of any study-specific procedures, IC must be obtained from the subject. Likewise, privacy or health information protection regulation may require subjects to sign additional forms to authorize study sites to submit subject information to the study sponsor. The IC process must be conducted by the principal investigator or an authorized designee, and the IC Form and Authorization to Use and Disclose Personal Health Information/Research Authorization must be given to the subject in a language he/she is able to read and understand. The process of IC must be conducted without using coercion or undue improper influence on or inducement of the subject to participate by the investigator or other study site personnel. The IC process shall not waive or appear to waive subject's legal rights. The language used shall be as non-technical as possible and must be understandable to the subject and the impartial witness, where applicable.

The subject must have ample time and opportunity to read and understand the IC, to inquire about details of the study, and to decide whether or not to participate in the study. All questions about the study should be answered to the satisfaction of the subject.

When the subject decides to participate in the study, the IC must be signed and personally dated by the subject and investigator or authorized designee, as required by the IC, and ensured by the principal investigator or his/her authorized designee. The investigator will clearly mark clinical records to indicate that the subject is enrolled in this clinical investigation.

A copy of the IC and the Authorization to Use and Disclose Personal Health Information/Research Authorization, signed and dated as required by law, must be provided to the subject.

If the IC is obtained the same day the subject begins participating in study-related procedures, it must be documented in the subject's case history that consent was obtained prior to participation in any study-related procedures. It is best practice for the IC process to be documented in the subject's case history, regardless of circumstance.

The date the subject signed the IC and Authorization to Use and Disclose Personal Health Information/Research Authorization, as required by law, must be documented in the subject's medical records. Once consent is obtained, report adverse events/deaths, study deviations and subject exits as they occur. All subjects who sign the IC will be considered enrolled for the study.

For logistical and public safety issues (e.g., global pandemic), remote consenting and collection of baseline data will be allowed.

The original of the signed IC must be filed in the hospital/clinical chart and/or with the subject's study documents.

The IC and Authorization to Use and Disclose Personal Health Information/Research Authorization as required by law must be available for monitoring and auditing. Any Medtronic Field personnel supporting the implant procedure must be able to review the subject's signed and dated IC and verify its completeness prior to proceeding with the implant/programming data download. In the event the Medtronic Field personnel identifies the IC as being incomplete, the implant procedure will not be allowed to occur until the consent of the subject can be adequately and appropriately obtained.

Consistent with the DoH, vulnerable adults (i.e., those subjects mentally incapable of giving consent) are excluded from this protocol. Any subjects with mental incompetence (e.g., Alzheimer's, dementia, psychiatric disorders, developmental disorders) should be assessed for vulnerable status. If the IC is signed by an individual other than the subject, the monitor may discuss whether the Investigator believes the subject meets the definition of a vulnerable adult. This protocol defines vulnerable adult as those subjects mentally incapable of giving consent, in the Investigator's opinion. The Investigator should consider the definition of vulnerable adult per ISO 14155, which defines vulnerable adults as: "individuals who are unable to fully understand all aspects of the investigation that are relevant to the decision to participate, or who could be manipulated or unduly influenced as a result of a compromised position, expectation of benefits or fear of a retaliatory response. For example, this could include Individuals with loss of autonomy due to immaturity or through mental disability, persons in nursing homes, children, impoverished persons, subjects in emergency situations, ethnic minority groups, homeless persons, nomads, refugees, and those incapable of giving IC. Other vulnerable subjects could include, for example, members of a group with a hierarchical structure such as university students, subordinate hospital and laboratory personnel, employees of the sponsor, members of the armed forces, and persons kept in detention.

10.7 Device Programming

Subjects are recommended to be set to Therapy Schedule #1 (30 minutes of stimulation every other day) until the 6-month follow-up visit. Following the 6-month follow-up visit, any of the 9 preset Therapy Schedules may be set.

For visits requiring the collection of programming and device data (e.g., Session Report, Usage Report) starting at the first visit following the device implant, data must be either transferred to Medtronic using the application on the handset and/or collected on the programming worksheet provided.

10.8 Device Explants

If the device is required to be explanted, a system modification visit will be completed. If the subject has the device explanted and a replacement is not anticipated to be implanted, the subject will complete a 1-month phone call. Following the call, the subject will be exited from the study after all related AEs have been resolved or remain unresolved based on the Investigator's determination with no further action planned.

It is recommended that all explanted devices be returned to Medtronic for analysis when permissible by local laws and regulations. See Section 7 for final product disposition details.

In the event that a subject has a re-attempt after a previous unsuccessful system modification, the subsequent attempt(s) must be reported via eCRF as separate system modifications.

10.9 Assessment of Efficacy

Voiding Diaries should be completed prior to or directly after the follow-up visit when data are collected. Site personnel should review forms for completeness.

Urinary Voiding Diary

Symptoms related to OAB will be evaluated using paper voiding diaries. Subjects will be trained to complete the urinary voiding diaries for 3 days with diary details collected (such as date, time, type of episode, urgency using the IUSS scale¹⁷ nocturia, etc.) as part of the baseline procedures by appropriately trained, qualified and delegated site personnel. The urinary voiding diaries will be completed for 3 days prior to each subsequent follow-up visit starting at the 1-month follow-up visit (or immediately following if not completed prior). Every effort should be made to remind subjects of the importance of real-time diary completion.

10.10 Assessment of Quality of Life

Subject assessments will be administered by appropriately trained, qualified, and delegated site personnel according to the usual practices of the site. Subjects will complete the study questionnaires confidentially on paper forms without site personnel consultation during the visit and these data will be entered into the EDC by site personnel.

Overactive Bladder Quality of Life Questionnaire (OAB-q)

The Overactive Bladder Quality of Life Questionnaire (OAB-q) is a 33-item validated questionnaire that was developed to assess symptom bother and the impact of overactive bladder (OAB) on health-related quality of life (HRQL)¹⁸. The questionnaire used in the current study includes a 4-week recall for symptom assessment. The questionnaire includes an HRQL Total score (comprised of the 4 domains: coping, concern, sleep, and social) and a symptom bother score.

[REDACTED]

[REDACTED]

[REDACTED]

[REDACTED]

[REDACTED]

[REDACTED]

**Urgency Perception Scale (UPS)**

The Urgency Perception Scale (UPS) is a single item questionnaire measure of perceived urinary urgency with three response options^{22,23}.

10.11 Assessment of Safety

All adverse events and device deficiencies (see Section 12) will be collected throughout the study once the informed consent form is signed until the subject is exited from the study.

10.12 Recording Data

Data entered must be traceable to source documents. Source documentation is defined as the first time data appear, and may include original documents, data, and records (e.g., hospital records, clinical and office charts, procedure reports, laboratory notes, memoranda, subjects' diaries, recorded data from automated instruments, copies or transcriptions certified after verification as being accurate copies, ultrasound images, subject files, device data and records kept at other departments involved in the study).

In general, eCRFs (or paper copies) may not serve as source documents, unless specified below. Source documentation for data elements not routinely captured in medical records may vary from study site to study site; the study site may use source document worksheets.

The investigator must ensure the availability of source documents from which the information on the eCRFs was derived. The type and location of source documents should be documented. Where printouts of electronic medical records are provided as source documents, or where copies of source documents are retained as source documents, they should be certified. Certification must contain (1) the signature of the individual making the copy, (2) the date the copy was made and (3) a statement attesting to the accuracy and completeness of the copy.

The source documents must be made available for monitoring or auditing by Medtronic's representative or representatives of the competent authorities and other applicable regulatory agencies.

The CRF may be considered source for the following data collection elements:

- Enrollment Notification: Study site assigned subject identifier
- Baseline: Administrative information
- Device Accountability eCRF: All device accountability data points

- AE eCRF: Date study site became aware of event, Relatedness of adverse event, System modification information, Common Terminology Criteria for Adverse Events Classification
- DD eCRF: Date study site became aware of event
- Deviations: Reason for deviation

Electronic Data Capture (EDC)

The Electronic system which is 21CFR§11 Part E compliant controls user access and ensures data integrity. This system is a fully validated system. The EDC system maintains an audit trail of entries, changes, or corrections in eCRFs. User access will be granted to each individual based on his or her delegation of authority and completion of required training. The system which allows the study centers to enter study data into the sponsor's database over a secure internet connection, will be used to capture study required Case Report Form (CRF) information. Data reported on urinary voiding diaries and subject questionnaires will be entered into the database by site personnel.

Electronic CRFs (eCRFs) will be provided by the sponsor; required data will be taken from source documents and directly entered into the study database via the eCRFs by the site personnel, in accordance with applicable regulations.

The Principal Investigator, Sub-Investigator, or an individual delegated by the Principal Investigator on the Delegation of Authority and Signature Form, are responsible for documenting and entering data for the study on the eCRFs. The Principal Investigator or Sub-Investigator is required to approve all data on eCRFs via electronic signature.

Programming and Device Data

Programming and device data (e.g., Usage Report, Session Report) will be collected in accordance with instructions provided prior to the subject leaving the visit and transferred to Medtronic using the application on the handset and/or collected on the programming worksheet provided.

Urinary Voiding Diaries

Symptom data for this study will be collected using paper voiding diaries.

The paper voiding diary collects details associated with symptoms for each episode. Diaries are to be completed only by the subject. The data will be entered to the EDC database by center personnel. Center personnel may not make entries to the diaries or questionnaires except for data fields confirmed by the subject as documented within source documentation.

10.13 Deviation Handling

A study deviation is defined as an event within a study that did not occur according to the CIP.

Prior approval is not required when a deviation is necessary to protect the safety, rights, or well-being of a subject in an emergency or in unforeseen situations beyond the investigator's control (e.g., subject failure to attend scheduled follow-up visits, inadvertent loss of data due to computer malfunction, inability to perform required procedures due to subject illness).

For medically justifiable conditions which preempt a subject's ability to complete a study-required procedure, it may be permitted to report only one deviation which will apply to all visits going forward. This may also apply for other unforeseen situations (e.g., the subject permanently refuses to complete a study required procedure and the data will not contribute to the primary end point analysis). However, prior approval from Medtronic is required for such situations.

All study deviations must be reported on the eCRF regardless of whether medically justifiable, pre-approved by Medtronic, an inadvertent occurrence, or taken to protect the subject in an emergency. Multiple deviations of the same type at the same visit may be reported on a single form in the database.

In the event the deviation involves a failure to obtain a subject's consent or is made to protect the life or physical well-being of a subject in an emergency, the deviation must be reported to the IRB as well as Medtronic within five (5) working days. Reporting of all other study deviations should comply with IRB policies and/or local laws and must be reported to Medtronic as soon as possible upon the study site becoming aware of the deviation. Reporting of deviations must comply with IRB policies, local laws, and/or Regulatory Authority requirements. Refer to Table 11: Investigator reports applicable per Medtronic requirements for deviation reporting requirements and timeframes for reporting to Medtronic and/or FDA.

Medtronic is responsible for analyzing deviations, assessing their significance, and identifying any additional corrective and/or preventive actions (e.g., amend the CIP, conduct additional training, terminate the investigation). Repetitive or serious investigator compliance issues may result in initiation of a corrective action plan with the investigator and study site, and in some cases, may necessitate suspending enrollment until the problem is resolved or ultimately terminating the investigator's participation in the study.

Examples of study deviations include but are not limited to:

- Failure to obtain proper IC
- Failure to collect required study data (e.g., required study diary)
- Inclusion/exclusion criteria not met

10.14 Subject Exit, Withdrawal or Discontinuation

Subjects are free to voluntarily withdraw from the study at any time and for any reason. All implanted subjects will be followed until the 24-month follow-up visit, unless withdrawn from the study.

Withdrawn or exited subjects will be followed by the Investigator (if still implanted with the study

device) or any physician in accordance with standard of care if the subject has been explanted and is seeking other treatments for OAB.

Examples of reasons for study discontinuation include, but are not limited to, those listed below:

- Subject death
- Subject lost to follow-up
- Subject voluntarily withdraws from the study
- Investigator terminates the subject's participation in the study due to lack of compliance, violation of/change in eligibility criteria
- Any clinical laboratory abnormality, current illness, or other medical condition or situation occurs such that continued study participation would not be in the best interest of the subject.
- Normal study completion

Prior to deeming a subject lost to follow-up, telephone calls must be documented in the subject's medical record. When subjects are lost to follow-up the investigator will make efforts to confirm the vital status of the subject. If a minimum of three attempts to contact the subject have failed (e.g., phone and mailed letter), and no response is received, the site should exit the subject and complete the Study Exit eCRF. When subjects are lost to follow-up the investigator will make efforts to confirm the vital status/health status of the subject as described in the informed consent

When a subject is withdrawn (exited) from the study, the Study Exit eCRF is to be completed and should include detailed notes as to why the subject was withdrawn from the study (e.g., discomfort, lack of efficacy, diary too burdensome).

If the subject has the device explanted and a replacement is not implanted, the subject must be exited from the study after all related AEs have resolved. Withdrawn subjects will not be replaced. All components of the investigational system should be returned unless instructed by Medtronic to dispose of product at the institution.

Once a subject completes participation in the study, the subject will be given guidelines for continued therapy use. Any device, procedure and/or therapy related adverse events and all product complaints should continue to be reported until the product is explanted.

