Statistics	The primary objective will be met by the percentage of subjects who are considered a UUI responder which is statistically superior to a performance goal of 40%. To determine responder status, the 3-day urinary voiding diary data at baseline and the 6-month follow-up visit will be used to determine daily urinary urge incontinence episodes per subject. Each subject's daily values at baseline and at 6 months will be compared to the UUI responder definition to determine if the subject is a responder. The UUI responder rate, corresponding two-

sided 95% confidence interval, and p-value from the comparison to the 40% performance goal will be calculated.

All p-values will be reported as 2-sided tests with alpha=0.05. The primary objective will be tested with a binomial test or a Z-test, depending on the use of imputation. If the primary objective is passed, the secondary objectives will each be tested using the Hochberg multiple testing strategy using a t-test or Wilcoxon signed-rank test, depending on the normality of the data.

The sample size was estimated using a binomial distribution for a one-sided alpha=0.025 test to show a 15% increase for the proportion compared to a performance goal of 40%. Assuming the alternative hypothesis of 55% of subjects who are considered an UUI responder, a minimum of 121 implanted subjects achieves at least 90% power to reject a performance goal of 40%. Sample size was computed in PASS 19.

Primary and secondary objectives will be analyzed using the Full Analysis Set (FAS). The FAS includes all subjects, using the intention-to-treat (ITT) principle, who have device implant attempted. All attempts will be made to minimize missing data. If 5% of the data or fewer are missing for the analysis, no imputation will be used, and the data will be analyzed using the Complete Case analysis set. Otherwise, if missing data are observed, multiple imputation will be used for the primary and secondary objectives. In the case of non-normal secondary objective data imputation, last observation carried forward (LOCF) imputation may be needed to test the hypothesis. Sensitivity analyses will be completed for the primary and secondary objectives including using only subjects with outcome data at baseline and follow-up ("Complete Case Analysis") and using only those complete case subjects who received stimulation ("As Treated Analysis").

[REDACTED]
[REDACTED]

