5.1 Objectives

5.1.1 Primary Objective

To demonstrate that the percentage of subjects considered a UUI responder after 6 months of tibial neuromodulation exceeds a performance goal of 40%.

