9.2 Subject Enrollment

Eligible subjects will sign a study-specific informed consent form (ICF) at which time they will be considered enrolled. Each subject must meet all the inclusion criteria and no exclusion criteria to be eligible to participate in the study. Any subject not meeting eligibility criteria will be excluded from study participation and exited from the study. Site personnel must complete logs related to recruitment and enrollment as required by the study.

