10.14.1 Study Exit

A Study Exit eCRF is required for all subjects. Prior to exiting a subject from the study, it is recommended to follow the subject until all ongoing related AEs are resolved or unresolved with no further actions planned. Upon exiting from the study, no further study data will be collected, or study visits will occur for the subject. All data available through the time of the subject's exit will be used for analysis.

Subjects are urged to remain in the study as long as possible but may be exited from the study for any of the following situations:

- Subject lost to follow-up
- Subject death
- Subject did not meet inclusion/exclusion criteria
- Subject was not implanted with an investigational device
- Subject did not provide consent or data use protection authorization
- Subject chose to withdraw (e.g., consent withdrawal, relocation to another geographic location)
- Investigator deemed withdrawal necessary (e.g., medically justified, failure of subject to maintain adequate study compliance)
- Device explant with no planned replacement.

The following information should be collected at study exit:

- Date of exit
- Reason for exit

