14.1.1 Analysis Sets

All Enrolled analysis set: Includes subjects who completed the informed consent process.

Full Analysis Set (FAS): Includes subjects with an attempted implant. If all implant procedures are successful, this will be equivalent to the All Implanted Analysis set.

All Implanted Analysis set: Includes subjects who are implanted.

Complete Case analysis sets: Includes subjects who are implanted and provide outcome measures at both baseline and follow-up visits. This set is defined for each outcome measure at each follow-up visit.

The study requires subjects to have UUI to be implanted. UUI subjects are those who have ≥ 1 urinary urge incontinence episode per day at baseline. For analysis purposes, Urinary Frequency (UF) subjects are those who have ≥ 10 urinary frequency episodes per day at baseline and all subjects will be considered to have urinary urgency since all eligible subjects have UUI. Some supportive, secondary objective, and additional measure analyses may use different definitions or subsets of the analysis sets listed above (e.g., changed assumptions for those subjects considered to have either UUI or UF).

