14.7 Sample Size Determination

The sample size for the primary objective was estimated using a binomial distribution for a one-sided alpha=0.025 test to show a 15% increase for the proportion compared to a performance goal of 40%. Assuming the alternative hypothesis of $\geq 55\%$ of subjects who are considered an UUI responder, a minimum of 121 implant attempted subjects achieves at least 90% power to reject a performance goal of 40%. The primary objective will have at least 88% power for any alternative hypothesis that is at least 15% larger than a performance goal. Secondary objectives are also expected to be adequately powered based on this sample size.

Assuming a $\sim 40\%$ attrition rate before implant, up to 200 subjects will be consented to achieve at least 121 subjects with implant attempted. Enrollment will be closed once the number of completed implants reaches 121; all enrolled subjects who meet eligibility criteria may be implanted (not to exceed 130 total implants). Implant attempted subjects who exit from the study will not be replaced.

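### An implanted subject may be exited for violated or changed eligibility and no study data are collected afterwards, so a member of the Full Analysis Set can lose the 6-month outcome through a discretionary decision

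*Protocol*

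**What the plan says.** Five places in the protocol bear on the point.

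- **10.14 (Subject Exit, Withdrawal or Discontinuation)** sets follow-up to the 24-month visit as the default for implanted subjects. Among its examples of reasons for discontinuation is the investigator terminating a subject's "participation in the study due to lack of compliance, violation of/change in eligibility criteria".
- **10.14.1 (Study Exit)** urges subjects to stay but says they may be exited for several reasons. Not having met the inclusion/exclusion criteria is one; not having been implanted is a separate one. It adds: "Upon exiting from the study, no further study data will be collected, or study visits will occur for the subject". Data up to exit are kept and analysed.
- **9.2 (Subject Enrollment)**: "Any subject not meeting eligibility criteria will be excluded from study participation and exited from the study". Section 6 has a parallel sentence placed next to the step to implant; 9.2 has no such limit.
- **10.13 (Deviation Handling)** lists "Inclusion/exclusion criteria not met" as an example of a study deviation.
- **14.1.1 (Analysis Sets)** defines the Full Analysis Set (FAS): "Includes subjects with an attempted implant". SAP 7.1.3 agrees.

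On missing outcomes, protocol 14.1.2 and SAP 7.4 use the Complete Case set without imputation when 5% or less is missing. Above that they use multiple imputation with baseline and Month 1, 2, 3 and 6 diaries. Protocol 14.4.1 and SAP 7.9.1.1 add a tipping point analysis. They also add a sensitivity analysis that assigns failure to certain subjects within the Complete Case set.

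**The concern.** Section 10.1 requires eligibility to be confirmed before implant, so a change in eligibility will normally come later, often in a subject who is already implanted. No passage says when an implanted subject with an eligibility problem is recorded as a deviation and kept, and when the subject is exited. Two sites could treat the same case differently.

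The study is single-arm and open-label, and site staff review the diaries and enter them (10.9, 10.12). An exit decision can therefore be made with knowledge of response. Some exclusion criteria in 9.4, such as urinary retention or compromised skin at the implant site, could arise after implant and resemble risks listed in 11.1. That overlap is an inference; the protocol does not state it.

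At stake is the primary comparison with the 40% performance goal. If such exits occur before month 6 and are more common among non-responders, the observed responder rate is too high. The lost outcomes could have been collected.

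**Working it through.** **Inputs.** The test was "estimated using a binomial distribution for a one-sided alpha=0.025 test to show a 15% increase for the proportion" (14.7). The null rate is 40% (5.1.1), the alternative 55% (Synopsis, Statistics), and n = 121 implant-attempted subjects (14.7). The switch to imputation is at 5% missing (14.1.2). The documents give no rate of exit after implant, so the number of exits k is an assumption.

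**Plan's own figure.** The critical count r is the smallest value with P(X ≥ r | n, 0.40) ≤ 0.025, where X is binomial. For n = 121, r = 60 and the exact tail is 0.0204. Power is P(X ≥ 60 | 121, 0.55) = 0.9009, so the stated power of at least 90% reproduces.

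**How many exits can drop out of the test.** 6/121 = 4.96% stays within the 5% rule; 7/121 = 5.79% does not. Up to six exits can therefore be left out without imputation, if nothing else is missing.

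**Effect on one result, if the exited subjects are non-responders.**

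| Responders / analysed | Rate | One-sided p | Result |
|---|---|---|---|
| 59/121 | 48.8% | 0.031 | fails |
| 59/119 (two exits dropped) | 49.6% | 0.0214 | passes |
| 57/121 | 47.1% | 0.067 | fails |
| 57/115 (six exits dropped) | 49.6% | 0.0236 | passes |

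**Effect on type I error.** Let the true FAS rate be 40% and let all k exits be non-responders. The rate among those analysed is 0.40 × 121/(121 − k) = 48.4/(121 − k).

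- k = 0: rate 0.400, r = 60 of 121, P(reject) = 0.020
- k = 3: rate 48.4/118 = 0.410, r = 59 of 118, P(reject) = 0.030
- k = 6: rate 48.4/115 = 0.421, r = 57 of 115, P(reject) = 0.064

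**Above 5% missing.** A rough upper illustration treats imputation as carrying no information beyond the completers, that is, a Z-test on completers with the sample variance. It gives 0.063 at k = 7 and 0.163 at k = 12. The planned model uses earlier diaries and should do better, by an amount the documents do not allow to be computed. Had the same subjects' outcomes been collected and shown non-response, the rule of at least 60 of 121 would give 0.018 at k = 7 and 0.016 at k = 12.

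**If exits are unrelated to response**, the cost is power only: 0.897 with 115 analysed and 0.853 with 109, against 0.901 with 121.

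**Which planned analyses would reveal it.** The failure-assignment analysis runs on the Complete Case set, which requires a follow-up outcome, so a subject who exited before month 6 cannot enter it. The Complete Case and As Treated analyses leave such subjects out for the same reason. Only the tipping point analysis addresses informative exits.

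**The case against.** A reader might infer that implanted subjects with an eligibility problem must be exited, that this defeats the intention-to-treat set, and that it removes subjects with device-related problems. The documents do not support any of these.

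- *Mandatory exit.* Section 10.14 gives examples and 10.14.1 says subjects may be exited. Only 9.2 says they will be, and it sits under the enrollment heading. The one mandatory device-related exit is explant without replacement, which is a separate rule.
- *Intention-to-treat.* Membership of the FAS depends on an attempted implant and survives exit. Data up to exit are used, and imputation draws on the subject's own earlier diaries.
- *Device problems.* No passage reapplies the exclusion criteria after implant, and several are worded for screening. Unanticipated pregnancy and an unhealed wound at day 7 are handled within the study (10.1), and a subject whose device is replaced keeps the original visit schedule.
- *Safety data.* Events before exit stay in the safety summaries, and 10.14.1 recommends following related events before exit.

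It is also fair that recording a deviation is compatible with a permissive exit, so 10.13 does not strictly contradict 10.14.1. The arithmetic would fit any informative dropout, and its exit counts are assumed. Finally, 10.14 and 10.14.1 also allow exit for illness, non-compliance or medical justification, so the same subject could leave by another line.

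These objections limit the size of the point. They do not answer it: a discretionary exit after implant is allowed on eligibility grounds, no study data follow it, and nothing says when the subject should instead be kept.

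**Conclusion.** The point holds as a gap in the exit wording that permits avoidable missing primary outcomes. It does not show that the analysis set is broken or that harmed subjects are systematically removed.

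The type I error of 0.064 with six exits, against 0.020 with none, is a bound. It assumes that every exited subject is a non-responder, that all six leave before month 6, that nothing else is missing, and that the true rate is exactly 40%. With fewer or less informative exits the effect shrinks, and with uninformative exits only power is lost. Since no exit rate is given, the likely size cannot be stated. The change is worth making because it is cheap and because neither imputation nor a tipping point analysis replaces outcomes that could have been observed.

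**What to change.** 1. In 9.2, 10.14 and 10.14.1, limit exit for unmet or changed eligibility to subjects without an attempted implant.
2. State that, after an attempted implant, an eligibility violation is recorded as a deviation under 10.13 and any later change in eligibility is recorded. With the subject's consent, diaries, questionnaires and adverse-event collection continue at least to month 6 and as scheduled to month 24.
3. Leave decisions on therapy or the device to the investigator, and record them separately from study exit.
4. Reconcile 10.14 with 10.14.1 on safety reporting. The first continues reporting of related events until explant once participation is complete; the second ends all study data collection at exit.

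The cost is protocol wording, site training, and a few more visits and diaries. No additional subjects are needed. The observed responder rate may be slightly lower. Because the other discretionary exit reasons remain, the change reduces this source of missing outcomes but does not close it.
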